3 ANALYSIS CONSIDERATIONS

3.1 Type of Analyses

The analyses and documentation described in this SAP are for the final analysis of the study.

3.2 Analysis Populations

3.2.1 Intent-to-Treat (ITT) Population

All patients who have enrolled into the study will be included in the Intent-to-Treat (ITT) population. Enrolled patient is defined as patient who signed the informed consent form and was not reported as a screen failure on the eCRF. Summaries of baseline characteristics and efficacy analyses will be done in the ITT population.

3.2.2 Safety Population

All patients who have received at least one dose of rilzabrutinib will be included in the Safety population. Summaries of adverse events and other safety parameters will be done in the Safety population.

3.3 Treatment Groups

3.3.1 Treatment Group Labels

The following treatment group labels will be used in the tables, listings and figures:

Treatment Group Label	Patients Included
Overall	All patients in the population will be included in this group.
Starting Dose 200 mg QD	Patients will be classified to these groups according to the starting
Starting Dose 400 mg QD	dose received. Each patient will be assigned to only one of these
Starting Dose 300 mg BID	groups.
Starting Dose 400 mg BID	
200 mg QD	Patients are evaluable in the dose group(s) if the dose level was
400 mg QD	received during the defined period (Sections 3.4.1and 3.5.2). Since
300 mg BID	most patients received more than one dose, a given patient can be
400 mg BID	assigned to multiple dose levels.
	For each of the following type of analyses, patients will be classified to
	each dose level based on:

Treatment Group Label	Patients Included
	 Dose level received prior to the visit for responder analyses, time-to analyses and analyses of proportion of patients meeting an endpoint, i.e., percent of weeks with platelet counts ≥ 50,000/μL. Dose level received at the onset of event for adverse events, and bleeding events analyses. Adverse events started after date of last dose of study drug will be attributed to the last dose level received. Dose level received during the time the medication was taken for any medication analyses. Medications taken after date of last dose of study drug will be attributed to the last dose level received.

3.4 Analysis Timepoints and Definitions

3.4.1 Observation Period

The observation period will be divided into 3 segments:

- 1) The **pre-treatment period** is defined as the period to the date of first dose of study drug.
- 2) The **on-treatment period** is defined as the period from the first dose of study drug to the last dose of study drug + 1. The on-treatment period includes the main treatment period and the LTE period.
 - Main on-treatment period is defined as from the date of first dose of study drug
 - to the date of the last dose of study drug + 1, if the patient did not enter LTE.
 - to the date before the first dose of study drug during LTE, if the patient entered LTE.
 Date of first dose in LTE is based on the date of dosing reported on C1D1_LTE Study
 Drug Administration eCRF.
- 3) The **post-treatment period** is defined as the period from the end of the on-treatment period. That is, the 4-week post treatment follow up period per protocol.

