# 10.10.4 Rescue Medication, DLTs, and Bleeding Scale Scores

The percentage of patients receiving rescue medication at each dosing level (Part A only) and at any time during dosing for Part A, and at any time during dosing for Part B.

15 May 2024

Version number: 1

The percentage of patients with a DLT will be summarized at each dosing level, overall for Part A, and overall for Part B.

Bleeding scale (IBLS) scores will be summarized over time at each dosing level, overall for Part A, and overall for Part B.

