2.1.4 Exploratory Objectives

2.2 Study Design

This is an adaptive, open-label, dose-finding study of rilzabrutinib in patients with ITP who are refractory or relapsed with no available and approved therapeutic options, with a platelet count <30,000/ μ L on two counts no sooner than 7 days apart in the 15 days before treatment begins.

Protocol amendments changed the active treatment period from 12 weeks to 24 weeks to >=24 weeks as follows:

In protocol version 7.0 (01 December 2017) the active treatment period is 12 weeks with a

- post-treatment safety follow up for a period of 12 weeks.
- In protocol version 8.0 (24 August 2018) the active treatment period is 24 weeks with a post-treatment safety follow up for a period of 4 weeks.
- In protocol version 9.0 (06 May 2019), patients who complete the active treatment period and demonstrate a platelet response defined as platelet counts ≥ 50,000/μL at ≥ 50% of the visits during the last 8 weeks of the active treatment would be allowed to enter the Long Term Extension (LTE) to receive study drug at the 400 mg BID dose. Patients may continue in the LTE until the patient is:
 - a) no longer responding per the LTE-defined platelet response and/or experiences dose limiting toxicities
 - b) the drug is no longer being developed by the Sponsor
 - c) the program is stopped for safety reasons or
 - d) the drug becomes commercially available in the patient's country

Patients who had previously completed the study prior to this amendment, were responders per the LTE requirement and did not experience a Dose-Limiting Toxicity (DLT) were allowed to enroll into the LTE. To qualify for the LTE patients would still need to satisfy the protocol inclusion and exclusion criteria.

Each patient is enrolled in the study and allowed to up-titrate their dose after 28 days of rilzabrutinib therapy, at each dose level, if they do not experience a platelet response (as defined in section 6.2 of the protocol) or a DLT at the last dose level. If the patient experiences a platelet response in the first 28-day cycle, at any one dose level but does not have a platelet response in the second cycle at that dose, they may dose escalate at the end of the second cycle. Patients experiencing a platelet response (as defined for the primary endpoint) will not have their dose escalated at the next cycle.

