2.5 Protocol Versions

Study enrollment started on protocol version 7.0 and the current protocol version is version 14.0 dated 12 Aug 2020.

Protocol Version	Version Date
Version 7	01 Dec 2017
Version 8	24 Aug 2018
Version 9	06 May 2019
Version 10	27 Sep 2019
Version 11	24 Oct 2019
Version 12	05 Dec 2019
Version 13	05 Mar 2020
Version 14	12 Aug 2020

^{*} Unless a sustained platelet response is seen or a DLT, in which case 3 extra patients are added to that group. A starting dose level may be dropped for futility after 3 or 6 patients are evaluated, or retained if efficacy is observed.

^{**} Individual patients will not dose-escalate when there is a platelet response at a lower dose level or toxicity (see dose-escalation rules). If several dose levels are therapeutic, some or all patients may not reach the higher dose levels.

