2.6 Protocol Amendments

In version 8.0 of the protocol, the study drug treatment and post treatment follow-up were changed from 12 weeks to 24 weeks, and 12 weeks to 4 weeks, respectively.

A 24-week treatment period is supported by completed long term good laboratory practice (GLP) animal safety toxicology studies (Investigator Brochure Version 9.)

In version 9.0 of the protocol, patients who entered into LTE will be monitored weekly for 6 months, then monthly for six months ad every three months thereafter.

In version 10.0 of the protocol, the 400 mg tablet was introduced for patients who enter the long term extension and definition of abstinence was added to inclusion criterion #6 a.

Cogstate testing was removed from protocol version 11.0.

In version 12.0 of the protocol, the planned number of patients was increased from 40 to 60 patients.

In version 13.0 of the protocol, Part B, an expansion of the study that will investigate the safety and efficacy of only the selected dose of 400 mg BID was added. Part B will enroll patients with ITP who have relapsed or have an insufficient response to prior therapies.

In version 14.0 of the protocol, the response criteria for entrance into the LTE from Part A were further defined. Part B stopping rules and study endpoints were updated to reflect discussion with FDA. Part A unneeded weighted logistic regression analysis was removed.

Page 15 of 57

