3.4.3 Study Visits

For protocol version 7.0, the study visits are:

- Screening
- Cycle X Day 1, Cycle X Day 8, Cycle X Day 15 and Cycle X Day 22, where X <= 3
- Day 85 (Last day of active rilzabrutinib treatment)
- Day 113 (Follow-up visit)
- Day 141 (Follow-up visit)
- Day 169 (End of Study visit)
- Early Withdrawal
- Unscheduled visit
- Laboratory Only Visits for Hematology, differential & retics: Days 92, 99, 106, 120, 127, 134, 148, 155, 162 and 169) (Follow-up visit)

For protocol version 8.0, the study visits are:

- Screening
- Cycle X Day 1, Cycle X Day 8, Cycle X Day 15 and Cycle X Day 22, where X ≤ 6
- Day 169 (Last day of active rilzabrutinib treatment)
- Day 197 (End of Study visit)
- Early Withdrawal
- Unscheduled visit
- Laboratory Only Visits for Hematology, differential & retics: Days 176, 183 and 190) (Follow-up visit)

For protocol version 9.0 to version 14.0, the study visits are:

- Screening
- Cycle X Day 1, Cycle X Day 8, Cycle X Day 15 and Cycle X Day 22, where X ≤ 10
- LTE: LTE Cycle X Day 1, LTE Cycle X Day 8, LTE Cycle X Day 15 and LTE Cycle X Day 22, where X ≤ 6
- LTE monthly visit: LTE Cycle X Day 1, where $7 \le X \le 12$
- LTE every 3 months visit: LTE Visit X, where $X \ge 1$ (until patients no longer on study)
- Last day of active rilzabrutinib treatment
- End of Study
- Early Withdrawal
- Unscheduled visit
- Laboratory Only Visits for Hematology, differential & retics: Days 176, 183 and 190) (Follow-up visit)

All scheduled visits will be used for descriptive summary. Unscheduled visits will be included in the derivation of 'Last value on-treatment' defined in section 3.4.4.

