5.1.5 Prior and Concomitant Medications

All medications will be coded according to the WHODRUG dictionary WHO-DDE B2, September 2017.

The following medications will be summarized by Level 4 classification and preferred name for ITP and rescue medications, and by Levels 2 and 3 classifications for other medications for each starting dose and overall:

- Prior ITP medications
- Other prior medications

Concomitant and post-treatment medications will be summarized for each dose level and overall:

- Non-rescue ITP medications taken during the main on-treatment period
- Non-rescue ITP medications taken during the LTE on-treatment period
- ITP medications taken post treatment period
- Rescue medications taken during the main period
- Rescue medications taken during the LTE period
- Other concomitant and post-treatment medications taken during the main period
- Other concomitant and post-treatment medications taken during the LTE period

Medications will be attributed to the dose level where the medication is taken during the dose level. The same medication may be attributed to more than one dose level. Medications started after the date of last dose of study drug will be attributed to the last dose level received.

Separate listings will be provided for each category of medications.

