5.5.1 Adverse Events

TEAEs will be attributed to the dose level where the AE start date is on or after the start date of that dose level and before the next dose level if applicable. TEAEs started after date of last study drug dosing will be attributed to the last dose level received.

The following summaries of adverse events will be provided:

	All patients		
	(By Dose Level		
	and Overall)	LTE patients	
		Main + LTE	
Summary	Main Period	Period	LTE Period
Overview of adverse event profile: Treatment			
emergent adverse events	X	X	X
TEAEs by primary SOC and PT (number of patients,			
number of events and event rate)	X	X	Х
TEAEs reported in >=5% patients by PT in descending			
order (number of patients)	Χ		
TEAE leading to study drug discontinuation by			
primary SOC and PT (number of patients)	X	X	X
TEAE leading to death by primary SOC and PT			
(number of patients)	X		
Treatment emergent SAE by primary SOC and PT			
(number of patients)	X	X	X
TEAEs by the maximum intensity, primary SOC and			
PT (number of patients)	X	X	X
Related TEAEs by primary SOC and PT (number of			
patients, number of events and event rate)	X	X	Х
Related TEAEs by the maximum intensity grade,			
primary SOC and PT (number of patients)	X	X	Х
TEAEs intensity Grade>=3 by primary SOC and PT			
(number of patients)	X	X	Х
Bleeding events by primary SOC and PT (number of	X (for overall		
patients, number of events and event rate)	only)	X	Х
Related bleeding events by primary SOC and PT			
(number of patients, number of events and event	X (for overall		
rate)	only)	X	Х
Bleeding events (Intensity Grade 2 or higher) by			
primary SOC and PT (number of patients, number of			
events and event rate)	X	X	Х
Related bleeding events (Intensity Grade 2 or higher)			
by primary SOC and PT (number of patients, number			
of events and event rate)	X	X	X
TEAEs by primary SOC and PT and by age group (<65,			
>=65 years) (number of patients)	X		

	All patients		
	(By Dose Level		
	and Overall)	LTE pati	ents
		Main + LTE	
Summary	Main Period	Period	LTE Period
TEAEs by primary SOC and PT and interquartile age			
group (number of patients)	X		
TEAEs by primary SOC and PT and by gender (male,			
female) (number of patients)	X		
TEAEs by primary SOC and PT and by concomitant			
ITP medications (No concomitant ITP medication,			
Corticosteroids alone, TPO-RA alone, Corticosteroids			
+ TPO-RA) (number of patients)	X		

[&]quot;X" represents a summary table will be provided.

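### The Part A SAP gives post-treatment follow-up as 4 weeks although version 7.0 patients had 12, and it charges off-drug events to the last dose level, so the crude by-dose rescue and bleeding proportions mix on-drug time with unequal off-drug time

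*SAP*

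**What the plan says.** Part A SAP section 3.4.1 starts the post-treatment period at the end of the on-treatment period and adds, with no reference to protocol version, "That is, the 4-week post treatment follow up period per protocol". Section 2.2 says version 7.0 had "post-treatment safety follow up for a period of 12 weeks". Section 2.6 says that in version 8.0 "the study drug treatment and post treatment follow-up were changed from 12 weeks to 24 weeks, and 12 weeks to 4 weeks, respectively". Section 2.5 confirms that "Study enrollment started on protocol version 7.0".

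The counting rules are these:

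- Section 3.4.2: the main safety period includes follow-up for patients who did not enter the long-term extension (LTE), and excludes it for those who did.
- Section 3.4.8: treatment-emergent events have a start but no end limit.
- Section 5.5.1: "TEAEs started after date of last study drug dosing will be attributed to the last dose level received". Section 3.3.1 gives the same rule for adverse event and bleeding analyses.
- Section 5.1.5: "Medications started after the date of last dose of study drug will be attributed to the last dose level received". That section restricts non-rescue ITP drugs to the main on-treatment period, but tabulates rescue over the main period, which includes follow-up.
- Sections 5.5.3 and 5.5.4: rescue and Grade 2 or higher bleeding are reported as simple proportions by dose level with Clopper-Pearson intervals.

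The protocol is narrower. Section 10.10 ties by-dose qualitative safety data in Part A to the time limits of each dose level. Section 10.10.4 reports rescue at each dosing level and "at any time during dosing for Part A".

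**The concern.** A proportion with at least one event depends on how long patients are watched. Here the time counted at a patient's last dose level is on-drug time plus an off-drug tail, and the planned length of that tail depends on protocol version and LTE entry. Both can be distributed unevenly across dose levels, so a difference in follow-up could appear in the tables as a difference between doses.

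Protocol section 1.3 gives a plasma half-life of 3-4 hours, so a bleed or rescue many weeks after stopping says little about the last dose. Characterising safety across the dose levels is the stated Part A safety objective. The SAP handles the version difference for efficacy, repeating the weeks-of-response summaries for version 7.0 and later patients separately (5.4.2.4, 5.4.2.5), but has no such split for safety. Its list of changes from the protocol (4.5) does not declare that off-drug events and rescue count towards a dose level.

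**Working it through.** **Step 1: follow-up length.** From the visit days in SAP 3.4.3, length = (end-of-study day − last treatment day) / 7.

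- Version 8.0: (197 − 169)/7 = 28/7 = 4 weeks. This reproduces the figure in 3.4.1.
- Version 7.0: (169 − 85)/7 = 84/7 = 12 weeks. This does not.

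**Step 2: off-drug time in the main safety period.** The SAP does not say whether the 4 weeks in 3.4.1 is a cap.

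- No cap (the better reading, since the period and the treatment-emergent definition are open-ended and 5.5 uses all study visits): 84 days, 28 days, and 0 days for patients who roll straight into the LTE. The first two differ by 84/28 = 3 times.
- Cap: 28, 28 and 0 days. The remaining 84 − 28 = 56 days of version 7.0 follow-up then belong to no defined period.

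**Step 3: off-drug share of time at the last dose level, without a cap.** Share = off-drug weeks / (weeks on last dose + off-drug weeks), for patients who escalate as in SAP Tables 1 and 2.

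| Path | Last dose | Share |
|---|---|---|
| Version 7.0, cohort 1 | 300 mg BID | 12/(4+12) = 75% |
| Version 7.0, cohort 2 | 400 mg BID | 12/(4+12) = 75% |
| Version 7.0, cohort 3 | 400 mg BID | 12/(8+12) = 60% |
| Version 7.0, cohort 4 | 400 mg BID | 12/(12+12) = 50% |
| Version 8.0, cohort 1, no LTE | 400 mg BID | 4/(12+4) = 25% |
| Version 8.0, cohort 4, no LTE | 400 mg BID | 4/(24+4) = 14% |
| Direct LTE entrant | any | 0% |

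**Step 4: possible effect on a proportion.** The documents give neither event rates nor the number of version 7.0 patients, so this is an assumed range. With a constant off-drug hazard, 12-week risk = 1 − (1 − 4-week risk)³. Four-week risks of 2%, 5%, 10% and 20% become 5.9%, 14.3%, 27.1% and 48.8%.

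At a 4-week risk of 10%, suppose a share s of the non-LTE patients whose last dose is at a given level are version 7.0. Their pooled off-drug risk is s × 27.1% + (1 − s) × 10%. For s = 25%, 50% and 75% this is 14.3%, 18.6% and 22.8%, against 10% under a common 4-week window.

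**The case against.** Several points on the other side stand.

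- **Patient-year rates are planned.** Section 5.5.1 reports rates per patient-year for treatment-emergent events and for bleeding, including Grade 2 or higher bleeding. This is partial relief: it does not cover rescue or the 5.5.4 proportion, and the SAP does not say whether by-dose patient-years include off-drug time. A separate post-treatment adverse event table exists, but only for the overall group.
- **The 12 versus 4 week contrast depends on the reading of 3.4.1.** A cap would remove it. It would also leave late version 7.0 events unplaced and keep the gap between LTE entrants and the rest, so the text needs repair either way.
- **Follow-up events must be assessed** (protocol 10.1), and rescue leads to discontinuation in Part A, so rescue near the last dose is relevant to that dose. Both are reasons to report such events separately, not to drop them.
- **On-drug time per level also differs by design,** and Part A is descriptive with no hypothesis testing. A date rule cannot equalise on-drug exposure, but it can remove the off-drug part.

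A reader might infer that these tables drove the choice of 400 mg BID. The dates do not support that: protocol version 13.0 (March 2020) already named it as the selected dose, and the first version of this SAP is dated November 2020. A reader might also take 75% against 14% as the typical contrast. Those are the two ends of the ranges, and cohort 1 was planned at only 3-6 starters out of about 60 patients. Three of the four version 7.0 paths end on 400 mg BID, so part of the extra off-drug time would count against the selected dose.

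**Conclusion.** The point holds as an internal contradiction in the Part A SAP and an undeclared departure from protocol sections 10.10 and 10.10.4. (The SAP was written against protocol version 14.0; the comparison here is with the current protocol.) Its main effect is on the crude by-dose proportions for rescue and for Grade 2 or higher bleeding.

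On the uncapped reading, planned off-drug windows are 84, 28 or 0 days, and the off-drug share of last-dose time is 50-75%, 14-25% or 0%. These figures assume patients follow the planned dosing paths and visit days. The effect on reported percentages cannot be fixed from the documents. Nor should it be inferred that every version 7.0 patient had 12 weeks off drug: the version 8.0 amendment history let patients still in the 12-week treatment period reconsent to 24 weeks.

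The primary responder analysis is not affected, because section 3.4.2 ends it one day after treatment. The change is worth making but does not undermine the main Part A conclusions.

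**What to change.** - In 3.4.1, give follow-up length by protocol version: 12 weeks for version 7.0 and 4 weeks from version 8.0. Make the follow-up term in 3.4.2 refer to it.
- In 5.1.5, 5.5.1, 5.5.3 and 5.5.4, base by-dose proportions on events or rescue that start on treatment: from the first dose at a level until the next level begins, or until the last main-period dose + 1 day. Say so explicitly for patients who completed the study and joined the LTE later, because 3.4.1 currently runs their main on-treatment period, including the off-drug gap, to the day before the first LTE dose.
- Show events and rescue starting in follow-up in a separate table by last dose level, limited to 28 days after the last dose for all versions. Use as denominator the patients who had that follow-up, so that direct LTE entrants with 0 days are not pooled with patients who had 28. List later version 7.0 events.
- State in 5.5.1 whether by-dose patient-years include off-drug time, and record in 4.5 any remaining difference from protocol 10.10 and 10.10.4.

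The cost is some SAP wording, a date filter and one extra table split, and a few late version 7.0 events move from a table to a listing. The Part B SAP says a Part A study report has been prepared, so in practice this may mean supplementary tables.

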3.4.2 Analysis Period

There are primarily 3 analysis periods for safety analyses:

- 1) Main period is
 - Main on-treatment period + FU, if the patient did not enter LTE
 - Main on-treatment period only, if the patient entered LTE
- 2) LTE period is LTE on-treatment period + FU
- 3) Main and LTE period combined, if the patient entered LTEs

Efficacy analyses will be based on on-treatment period (i.e., up to end of treatment +1 day), with the exception of descriptive analyses which will include post-treatment follow up visits.

3.4.3 Study Visits

For protocol version 7.0, the study visits are:

- Screening
- Cycle X Day 1, Cycle X Day 8, Cycle X Day 15 and Cycle X Day 22, where X <= 3
- Day 85 (Last day of active rilzabrutinib treatment)
- Day 113 (Follow-up visit)
- Day 141 (Follow-up visit)
- Day 169 (End of Study visit)
- Early Withdrawal
- Unscheduled visit
- Laboratory Only Visits for Hematology, differential & retics: Days 92, 99, 106, 120, 127, 134, 148, 155, 162 and 169) (Follow-up visit)

For protocol version 8.0, the study visits are:

- Screening
- Cycle X Day 1, Cycle X Day 8, Cycle X Day 15 and Cycle X Day 22, where X ≤ 6
- Day 169 (Last day of active rilzabrutinib treatment)
- Day 197 (End of Study visit)
- Early Withdrawal
- Unscheduled visit
- Laboratory Only Visits for Hematology, differential & retics: Days 176, 183 and 190) (Follow-up visit)

For protocol version 9.0 to version 14.0, the study visits are:

- Screening
- Cycle X Day 1, Cycle X Day 8, Cycle X Day 15 and Cycle X Day 22, where X ≤ 10
- LTE: LTE Cycle X Day 1, LTE Cycle X Day 8, LTE Cycle X Day 15 and LTE Cycle X Day 22, where X ≤ 6
- LTE monthly visit: LTE Cycle X Day 1, where $7 \le X \le 12$
- LTE every 3 months visit: LTE Visit X, where $X \ge 1$ (until patients no longer on study)
- Last day of active rilzabrutinib treatment
- End of Study
- Early Withdrawal
- Unscheduled visit
- Laboratory Only Visits for Hematology, differential & retics: Days 176, 183 and 190) (Follow-up visit)

All scheduled visits will be used for descriptive summary. Unscheduled visits will be included in the derivation of 'Last value on-treatment' defined in section 3.4.4.

